**Drug Availability**

**Commercial Agents: Daratumumab, Lenalidomide**

**Drug Company Supplied: None**

Document History	(Effective Date)
Activation	April 9, 2018
Amendment 1	June 13, 2018
Amendment 2	October 30, 2018
Amendment 3	July 24, 2019
Amendment 4	May 7, 2020
Amendment 5	June 22, 2020
Amendment 6	October 06, 2020
Amendment 7	December 01.2020
Amendment 8	February 26, 2021
Amendment 9	Pending

### Study Schema

If a patient is deemed ineligible or a cancel, please refer to Section 13 for follow-up information.

\*MRD Assessment (Day 100 or before the start of Maintenance if patient receives optional consolidation treatments) :  
Peripheral Blood (Next Generation Sequencing; NGS): Prior to cycle 1, 3 (or 5 in case cycles 3 and 4 given), at Day 100, prior to cycle 8, 12, 16, 18, 20 (or cycle 10, 14, 18, 20, 22 in case cycles 3 and 4 given)  
Bone Marrow (Multiparameter Flow Cytometry; MPF and NGS): Prior to cycle 1, 3 (or 5 in case cycles 3 and 4 given), at Day 100, prior to cycle 16 (or 18 in case cycles 3 and 4 given)

\*\*Cycle 1 (to 3, as the case may be for that patient) = 28 days (4 weeks)

Cycle 2 (or 4, as the case may be for that patient) = Up to 84 days (4 weeks treatment + window period up to 8 weeks between Consolidation 1 and ASCT)

Cycle 3 =Up to 124 days (Day 100 visit of ASCT occurs 90-110 days after ASCT + window period up to 14 days between Day 100 visit and start of Maintenance)

Cycles 4-15 (or 6-17, as the case may be for that patient) = 28 days (4 weeks)

Cycles 16 and beyond (or 18 and beyond as the case may be) = 90 days (3 months)

†In case patient given cycle 3 and 4 optional treatment in consolidation 1, the subsequent cycle numbers will be adjusted accordingly.

Confirmation of PD is not required. However, treatment may be discontinued for progressive disease that is unconfirmed per physician discretion. In this case, an objective status of PD should be entered on the measurement form and progressive disease should be reported on the event monitoring form.

Generic name: Daratumumab Brand name(s): Darzalex® Mayo Abbreviation: Dara Availability: Commercial	Generic name: Lenalidomide Brand name(s): Revlimid® Mayo Abbreviation: REVLIMID Availability: Commercial
--	---

## 1.0 Background

### 1.1 Multiple Myeloma

Multiple myeloma (MM) is a malignant disorder of the plasma cells, characterized by uncontrolled and progressive proliferation of a plasma cell clone. The disease leads to progressive morbidity and eventual mortality by lowering resistance to infection and causing significant skeletal destruction (with bone pain, pathological fractures, and hypercalcemia), anemia, renal failure, neurological complications and hyper viscosity syndrome.

The majority of patients with MM produce a monoclonal protein, also called paraprotein, M-protein or M-component, which is an immunoglobulin (Ig) or a fragment of one that has lost its function. Normal immunoglobulin levels are compromised, leading to susceptibility of infections. The proliferating MM cells displace the normal bone marrow leading to dysfunction in normal hematopoietic tissue and destruction of the normal bone marrow architecture, which is reflected by clinical findings such as anemia, paraprotein in serum or urine, and bone resorption seen as diffuse osteoporosis or lytic lesions shown in radiographs. Furthermore, hypercalcemia, renal insufficiency or failure, and neurological complications are frequently seen. A small minority of patients with MM are non-secretory.

At the time of diagnosis, multiple myeloma is a heterogeneous disease, with a course that varies on the basis of both disease- and host-related factors (e.g., age, renal function, stage, chromosomal abnormalities). Multiple myeloma causes significant morbidity and mortality. It accounts for approximately 1% of all malignancies and 13% of hematologic cancers. Approximately 50,000 patients per year are diagnosed with multiple myeloma in the EU and US, and 30,000 patients per year die due to multiple myeloma.

### 1.2 Treatment for Multiple Myeloma

Treatment choices for MM vary with age, performance status, comorbidity, the aggressiveness of the disease, and related prognostic factors. Newly diagnosed patients with MM are typically categorized into 2 subpopulations usually defined by their age and suitability for the subsequent approach to treatment. Younger patients will typically receive an induction regimen followed by consolidation treatment with high-dose chemotherapy and autologous stem cell transplantation (ASCT). For those not considered suitable for high-dose chemotherapy and ASCT, longer-term treatment with multi-agent combinations including alkylators, high-dose steroids, and novel agents are currently considered as standards of care.

Over the past few years several novel treatments (immunomodulatory drugs; IMiDs and proteasome inhibitors) have become available for patients with MM. Although higher percentages of patients are achieving remission, all patients eventually relapse and become resistant to therapy. Novel agents and new combinations regimens are needed for improved outcome in this disease. There is an increasing body of evidence suggesting that clinical or laboratory parameters may be important in selecting specific treatment options for patients with MM. This is further important since the novel agents being used for the treatment of MM have their own inherent side effect profiles that are unique and need specific management as against the more expected adverse events from conventional chemotherapeutic agents. This is especially true in elderly patients who may

have other comorbidities, since the median age at diagnosis for MM is 70 years. Thus, there is a constant need to develop newer, better-tolerated agents/regimens that can keep the disease controlled for prolonged durations as well as be safe with respect to low cumulative toxicities.

### 1.3 Role of Daratumumab in Multiple Myeloma

Daratumumab is an immunoglobulin G1 kappa (IgG1k) human monoclonal antibody (mAb) that binds to a unique CD38 epitope on CD38-expressing cells with high affinity. It was developed by the immunization of human immunoglobulin transgenic mice with recombinant CD38 protein. CD38 is a 46-kDa type II transmembrane glycoprotein that is highly expressed on MM cells. CD38 has various mechanisms including ectoenzymatic activity, receptor-mediated regulation of cell adhesion and signal transduction. Preclinical studies have shown that daratumumab induces MM cell death through several mechanisms, including complement-dependent cytotoxicity (CDC), antibody-dependent cell-mediated cytotoxicity (ADCC), antibody-dependent cellular phagocytosis (ADCP), and FcR mediated-crosslinking inducing apoptosis. In a combined analysis of GEN501 and SIRIUS studies including 148 patients, the Overall Response Rate (ORR) was 31 %, and at a median follow-up of 14.8 months, the estimated Overall Survival (OS) was 19.9 months. These trials demonstrated that daratumumab is active as monotherapy in patients with heavily pre-treated and relapsed/refractory myeloma (RRMM) alongside maintaining its anti-myeloma activity in previously treatment refractory patients as evident by ORR 33 and 29.7 % in GEN501 and SIRIUS, respectively. Preclinical studies have shown that Daratumumab in combination with other agents enhances the antimyeloma activity and now there are reported multiple phase II /III trials to study the same. These include data from the CASTOR and POLLUX trials of the combination of daratumumab and dexamethasone with bortezomib and lenalidomide, respectively, showing enhanced efficacy of these regimens in patients with early relapsed MM (2nd or 3rd line) and low minimal residual disease (MRD) states leading to the FDA approval of these regimens.

### 1.4 Role of ASCT and Post-ASCT Maintenance Therapy in Multiple Myeloma

ASCT is the standard of care in transplant-eligible MM patients based on several phase III trials and meta-analyses depicting significant improvement in progression free Survival (PFS), CR, and OS. Attal et al in IFM-90 trial reported superior outcomes of high-dose chemotherapy (HDC) followed by ASCT compared to conventional chemotherapy alone, with improved OS (57%), CR (22%) and event-free survival (EFS) (16%), and median OS 57 months versus 44 months. The majority of post-ASCT patients relapse with median PFS around 36 months. Relapses are harder to treat and prognosis gets worse with each relapse. Multiple studies have suggested a survival advantage from attaining a deeper response to induction chemotherapy and ASCT, and sustained CR was shown to be a surrogate for OS in MM population. The clinical significance of MRD negativity using highly sensitive methods has been reviewed and goal of MRD is to stratify the risk and evaluate the response to novel agents. Despite remarkable improvement in treatment outcome in MM with the use of IMiDs and novel agents, it remains an incurable disease. Multiple studies in the last few years have examined the role of consolidation and/or maintenance to eliminate MRD after HDC-ASCT in MM. Post-ASCT consolidation and/or maintenance strategies have been studied in multiple trials including single and combination agents including interferon-alpha,

glucocorticoids, thalidomide, lenalidomide, bortezomib and combination regimens to determine compare PFS and OS to improve long term outcomes.

### 1.5 Minimal Residual Disease (MRD) in Multiple Myeloma

CR is defined as disappearance of clonal plasma cells in the bone marrow, and absence of paraprotein in urine and serum by immunofixation. Stringent CR (sCR) as defined by International Myeloma Workshop includes above mentioned parameters along with a normal kappa/lambda free light chain ratio. Molecular CR (mCR) defined as absence of detectable disease by polymerase chain reaction (PCR) for Ig gene rearrangement was associated with prolonged PFS and OS in allogeneic transplant patients and this extent of response was not achieved in autologous transplant patients. With the use of novel therapies, there was necessity to develop sensitive assays to detect and monitor MRD that will have prognostic implication in PFS and OS to compare between different consolidation and/or maintenance agents. Various methods include allele-specific oligonucleotide PCR (ASO-PCR), next-generation sequencing (NGS) and multiparameter flow cytometry (MPF) capable of detecting 1 clonal cell in  $10^6$  and 1 clonal cell in  $10^4$  normal cells, respectively. In a study of 102 MM patients, a comparison of CR detection by negative immunofixation (CR), normal serum free light chain ratio (sCR), and undetectable myeloma cells by MPF (immunophenotyping CR-iCR) treated with novel agents showed that 43% patients achieved CR, 30% achieved sCR, and 30% achieved iCR. Patients in iCR showed significantly improved PFS and TTP as compared to sCR versus CR with no significant survival difference between sCR versus CR patients. In this study ASO-PCR and MPF were able to detect MRD in 17 and 11 patients, respectively. PFS for those patients without versus with MRD detected by ASO-PCR was 34 versus 15 months, respectively ( $P=.04$ ) and by MPF was 27 versus 10 months, respectively ( $P=.05$ ). In order to predict unsustained CR, a study was conducted in 241 patients in CR at Day-100 after ASCT. It was found that presence of baseline high-risk cytogenetics by fluorescent in situ hybridization (HR 17.3;  $P<.01$ ), and persistent MRD by MPF at day-100 after ASCT (HR 8.0;  $P<.01$ ) were the only independent factors that predicted for unsustained CR and a poor outcome with a median OS of 39 months. Another study assessed MRD using MPF in post-induction and at day-100 post SCT as well as post-induction in transplant ineligible patients. This study demonstrates clinical utility of MPF as the patients with MRD had inferior outcomes as compared to those without detectable MRD. The same study also showed that maintenance therapy benefits the patients with MRD negativity and also can convert patients to MRD negative status. MRD may serve as a biomarker to inform MM therapy and MRD negativity becomes a goal of future studies.

### 1.6 Rationale of Daratumumab as a Consolidation Therapy before SCT and Maintenance Therapy in Post-SCT Settings for MRD Assessment

Our primary endpoint is to determine the percentage of patients with MRD negativity at Day 100 post SCT and at post-maintenance treatment for 1 year. Phase II multicenter single arm study was conducted in 10 IFM centers in France in 2009 to evaluate response after lenalidomide, bortezomib and dexamethasone (RVD) induction followed by SCT followed by 2 RVD consolidations and 1-year lenalidomide maintenance in 31 untreated transplant eligible MM patients. At the time of consolidation, 97% achieved PR, 87% at least VGPR, including 50% who achieved CR and among 26 evaluable patients, 15 (58%) were MRD negative. They evaluated MRD by bone marrow aspirate at post-induction/pre-ASCT, post-ASCT, post-consolidation and end of treatment regardless of

response. With lenalidomide, 5 patients experienced MRD improvement and after all treatment sequences, 21 patients (68%) achieved MRD negativity. Overall, there were high response rates and depth of response increased over the course of the transplantation program. Rate of VGPR increased from 58% after induction to 70% and 87% after transplant and consolidation, respectively. 1-year lenalidomide maintenance further improved MRD negativity. 3-year PFS was 100% for MRD negative patients. Further studies evaluated that MRD negativity is a major prognostic factor for clinical outcome and MRD negativity should be the goal for treatment of ASCT eligible patients in MM. Another study was conducted in 241 MM patients in 2 PETHEMA/GEM trials, GEM2000 (VBMCP [vincristine, carmustine, doxorubicin and dexamethasone followed by HDT/SCT and 2-year IFN and prednisone maintenance; n=140] and GEM-2005 <65 y (randomized induction with the same chemotherapy plus bortezomib in the last 2 cycles or thalidomide/dexamethasone or bortezomib/thalidomide/dexamethasone followed by HDT/SCT and 3-year maintenance with IF-2alphab or thalidomide or thalidomide/bortezomib; n= 101). TTP (median 71 months) and OS (71% at 5 years) were longer in CR patients than in less than CR patients at Day-100 after HDT/SCT (TTP; median 47 months and OS: 60% at 5 years). Multivariate analysis showed that the best predictive parameters for TTP were immunophenotypic CR status (MRD by MFC) and FISH cytogenetics. 16% of CR patients had high-risk disease and showed a significantly inferior TTP (3 years, 40% vs. 80%) and borderline OS (3 years, 73% vs. 96%) compared with standard risk patients. Persistent MRD in 87 (36%) out of 241 CR patients showed significantly inferior TTP (3 years 58% vs. 86%) and OS (3 years 80% vs. 90%). They further explored clinical impact of the immunophenotypic CR in standard and high-risk disease. Best prognosis was for patients with both standard-risk cytogenetics and achievement of immunophenotypic CR (3 years: TTP 94%, OS 100%), whereas worse outcome occurred in both high-risk disease and persistent MRD (3 years: TTP 0%, OS 32%). Of 241 patients, 29 (12%) were in unsustained CR within 1 year had persistent MRD by MFC (66% vs. 32%) as compared with the remaining patients.

## 1.7 Trial Design

This will be a phase II, open label, prospective clinical trial in MM patients with any induction treatment, who are considered eligible for an SCT and have detectable MRD. So far there have not been any clinical trials to determine the effect of daratumumab on MRD as a consolidation therapy in pre-ASCT setting and as maintenance therapy in post-ASCT setting. The reason to include patients with MM who have received any induction is that the aim of this trial is to assess the efficacy of daratumumab in the pre- and post-ASCT settings in improving the MRD-status of patients. Treatment dose in the maintenance portion (daratumumab+lenalidomide) will be fixed based on other prior clinical trials using this combination.

## 2.0 Goals

### 2.1 Primary Objective:

To determine the percentage of patients achieving MRD negativity by MPF after autologous stem cell transplant (SCT) (at Day 100) using pre-SCT daratumumab consolidation.

### 2.2 Secondary Objectives:

- 2.21 To determine percentage of patients achieving MRD negativity by MPF after 1 year of daratumumab+lenalidomide-based maintenance therapy.
- 2.22 To determine progression-free survival (PFS) for peri-SCT treatment with daratumumab.
- 2.23 To determine percentage of MRD negativity by MPF after pre-SCT consolidation with daratumumab.
- 2.24 To determine safety profile of peri-SCT daratumumab with lenalidomide.
- 2.25 To determine the overall response rate (ORR) of patients receiving peri-SCT daratumumab for MM.
- 2.26 To determine the overall survival (OS) for patients receiving peri-SCT daratumumab for MM.

### 3.0 Patient Eligibility

#### 3.1 Inclusion Criteria

- 3.11 Age  $\geq$ 18 years and considered transplant eligible.
- 3.12 Diagnosis: Pathologically confirmed diagnosis of multiple myeloma who are transplant eligible and have received any prior induction therapy (with or without maintenance).
- 3.13 Measurable MRD in bone marrow within 28 days prior to registration (MPF method)
- 3.14 ECOG Performance Status (PS) 0, 1, or 2 (Appendix I) at registration.
- 3.15 The following laboratory values obtained  $\leq$ 14 days prior to registration:
  - Absolute neutrophil count (ANC)  $\geq$ 1,000 cell/mm^3 without growth factor support
  - Platelets  $\geq$ 50,000 cells/mm^3 for patients who have bone marrow plasmacytosis  $<$ 50% or  $\geq$ 30,000 cells/mm^3 for patients who have bone marrow plasmacytosis of  $\geq$ 50%
  - Calculated or measured creatinine clearance  $\geq$ 30 ml/min (see Appendix II)
  - Total bilirubin  $\leq$ 1.5 x upper limit of normal (ULN) unless due to Gilbert's syndrome, in which case the direct bilirubin must be  $\leq$ 1.5 X ULN.
  - Aspartate aminotransferase (AST)/SGOT and alanine aminotransferase (ALT)/SGPT  $\leq$ 3 x ULN
  - PT/INR  $\leq$ 1.5 X ULN
  - Negative Urine or serum pregnancy test for women of childbearing potential.  
NOTE: Females of reproductive potential must adhere to the scheduled pregnancy testing as required in the Revlimid REMS® program.
- 3.16 Provide informed written consent.
- 3.17 Measureable disease of multiple myeloma as defined in section 11.1 at the time specified by one of the following:
  - If no relapse prior to transplant, values obtained at the time of diagnosis
  - If disease relapse prior to transplant and the patient did not have treatment for the relapsed disease prior to transplant, the values obtained at the time of relapse immediately prior to the transplant.
  - If disease relapse prior to transplant and the patient did have treatment for the relapsed disease prior to transplant, the values obtained prior to this therapy, ie, the time of relapse.

#### 3.2 Exclusion Criteria

- 3.21 Any previous ASCT for MM. **EXCEPTION:** Patient had autologous stem cell transplant  $>$  3 years ago without any related adverse events. (**NOTE:** Patient may have had prior stem cell collection before registration on the study)
- 3.22 Any prior therapy with daratumumab

3.23 Non-secretory MM or known AL amyloidosis

3.24 Clinically significant active infection requiring intravenous antibiotics ( $\leq 14$  days prior to registration).

3.25  $\geq$ Grade 3 neuropathy and/or POEMS syndrome (plasma cell dyscrasia with polyneuropathy, organomegaly, endocrinopathy, monoclonal protein, and skin changes).

3.26 Other prior malignancy.

**EXCEPTIONS:**

- Adequately treated basal cell or squamous cell skin cancer
- Any *in situ* cancer
- Adequately treated Stage I or II cancer from which the patient is currently in complete remission, or
- Any other cancer from which the patient has been disease free for at least three years

3.27 Concurrent therapy considered investigational.

**NOTE:** Patients must not be planning to receive any radiation therapy (except localized radiation for palliative care that must be completed prior to starting Cycle 1, Day 1).

3.28 Any of the following because this study involves an investigational agent whose genotoxic, mutagenic and teratogenic effects on the developing fetus and newborn are unknown:

- Pregnant women
- Nursing women (lactating females are eligible provided that they agree not to breast feed while taking lenalidomide)
- Men or women of childbearing potential who are unwilling to employ adequate contraception

3.29a Major surgery  $\leq 4$  weeks prior to registration.

3.29b History of stroke/intracranial hemorrhage  $\leq 6$  months prior to registration.

3.29c Clinically significant cardiac illness including New York Heart Association (NYHA) Class III or Class IV heart failure (Appendix III), unstable angina pectoris, myocardial infarction within the past 6 months, or  $\geq$ Grade 3 cardiac arrhythmias noted  $\leq 14$  days prior to registration.

3.29d Known HIV+ patients

3.29e Known Hepatitis B or Hepatitis C infection.

3.29f Exhibiting clinical signs of meningeal involvement of multiple myeloma.

3.29g Known severe chronic obstructive pulmonary disease or asthma defined as forced expiratory volume (FEV1) in 1 second less than  $<60\%$  of expected.

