- h) During treatment period, at end of treatment visit. The patient should be contacted by a nurse 30 days after the last dose of study treatment (or at the time of initiation of subsequent treatment if started before 30 days) to check if the patient has experienced any late adverse events. Grade 3 or higher adverse events at least possibly related to study treatment and deaths due to any cause should be reported as a late adverse event on the Survival and Disease Status Follow-Up/Event Monitoring form if they were not already reported on the Adverse Event form for the last cycle and they occurred prior to any subsequent treatment and 30 days post-end of treatment
- i) For females of childbearing potential, a negative pregnancy test (urine or serum) must be documented within 14 days of starting treatment on the study and for patients starting Cycle 4 (daratumumab+lenalidomide) in accordance with the REVLIMID REMSTM program. A female of childbearing potential (FCBP) is a sexually mature female who: 1) has not undergone a hysterectomy or bilateral oophorectomy; or 2) has not been naturally postmenopausal for at least 24 consecutive months (i.e., has had menses at any time in the preceding 24 consecutive months).
- j) Patients starting Cycle 4 treatment (daratumumab+lenalidomide) prior to starting treatment with REVLIMID
- k) To be collected at the end of every cycle of maintenance therapy while the patient is receiving lenalidomide
- l) UPEP testing required at baseline only. Subsequent testing will be as needed per physician discretion.

\*Repeat Electrophoresis of serum and urine, Serum immunoglobulins, Immunofixation serum and urine, and Immunoglobulin free light chain only if the assessments were not completed 14 days prior to End of Treatment visit.

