### 7.1 Treatment Schedule

#### 7.11 Consolidation 1 (Cycles 1-2 or 1-4, as the case may be for that patient)

Agent	Dose	Route	Day	Cycles
Daratumumab	16 mg/Kg* (IV) 1,800 mg (Injection)	IV or injection	1, 8, 15, 22	Cycle 1-2
Daratumumab	16 mg/Kg* (IV) 1,800 mg (injection)	IV or injection	1, 15	Cycle 3-4

Cycle 1 (to 3, as the case may be for that patient) length = 28 days;  
 Cycle 2 (or 4, as the case may be for that patient) length = up to 84 days (4 weeks treatment + window period up to 8 weeks between Consolidation 1 and ASCT)  
 Treatment Window (for patients receiving treatment through a local medical doctor)=  $\pm 5$  days

\*Any dose-adjustments will be made as per the prescriber information.

Daratumumab administration as per prescriber information and institutional guidelines.

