#### 7.12 Consolidation 2 (Cycle 3 or 5, as the case may be for that patient)

- All patients enrolled in the trial after completing consolidation 1 treatment will proceed to a SCT with Day 0 of SCT within 8 weeks of completing cycle 2 (or 4, as the case may be for that patient), Day 28 of consolidation 1.
- Stem cell collection could have been completed prior to initiating consolidation 1 or may be performed within the up to 8-week period between completion of Cycle 2 (or 4, as the case may be for that patient), Day 28 and Day 0 of SCT.
- Consolidation 1 should not be interrupted for the purpose of stem cell collection.
- SCT procedures should be completed as per institutional standards.
- Consolidation 2 period will be considered up until the Day 100 visit ( $\pm 10$  days as per institutional BMT program scheduling).
- Cycle 3 (or 5, as the case may be for that patient) length = Up to 124 days (Day 100 visit of ASCT occurs 90-110 days after ASCT + window period up to 14 days between Day 100 visit and start of Maintenance)

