#### 7.13 Maintenance (Cycles 4 and Beyond, or cycle 6 and beyond as the case may be for that patient)

- All patients will be initiated on maintenance therapy as below within 14 days of completing Day 100 visit post-SCT.

Agent	Dose	Route	Day	Cycles
Daratumumab	16 mg/Kg* (IV) 1,800 mg (Injection)	IV or Injection	1	Cycle 4-15 (or 6-17)
Lenalidomide	10 mg*	PO	1-21	Cycle 4-15

				(or 6-17)
--	--	--	--	-----------

Cycles 4-15 (or 6-17) length = 28 days

\*Any dose-adjustments will be made as per the prescriber information.

Daratumumab administrations as per prescriber information and institutional guidelines.

Note: Thromboprophylaxis is required as standard of care (see Section 9.3) for all patients on maintenance treatment.

- **NOTE:** Prior to Cycle 16 (or 18), patients who are still maintaining response will proceed to maintenance with single-agent daratumumab every 3 months till disease progression or unwanted adverse events, if any. Cycles 16 and beyond length = 90 days (3 months).
- In the event of disease progression, intolerable adverse event or patient refusal for continued therapy, they will proceed to event monitoring without any additional anti-MM therapy.
- Considering that there are newer immunotherapy compounds being made available for the treatment of multiple myeloma, based on the initial results of this clinical trial, amendments may be put in place to add more arms to the study with newer, proven safe combination regimens, especially for maintenance treatment.

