**ALERT:** **ADR reporting may be required for some adverse events (See Section 10)**

#### 8.1 General Considerations:

- Missed doses for lenalidomide are to be omitted rather than made up, unless the dose was forgotten and remembered on the same day, in which case the dose can be taken

that day. Any doses missed on a particular day are not to be made up the next day. Doses that are considered to be vomited are not to be made up and a mention about the time of dose and time of vomiting episode should be made in the pill diary.

- b) Daratumumab may be administered within  $\pm 1$  day of the scheduled dose if there are any logistical challenges (holiday, patient transport or other logistics, scheduling availability, etc.)
- c) If multiple toxicities are experienced, dose modifications will be based on the toxicity requiring the largest dose reduction.
- d) Reductions are based on the dose given in the preceding cycle and are based on toxicities with an attribution of possible, probable, or definite that were observed since the prior toxicity evaluation.
- e) If a drug is omitted due to specific adverse events and the patient is on combination therapy (maintenance therapy), the other agents, considered unrelated to the adverse event may be continued.
- f) If a patient cannot be administered a dose of daratumumab during Consolidation 1 (Cycles 1-2 or 1-4, as the case may be for that patient) for  $>28$  days due to adverse events or any other reason, the patient should be removed from the study treatment and go to event monitoring. (NOTE: Patients on maintenance therapy (cycles 4 and beyond, or cycle 6 and beyond as the case may be for that patient) may be continued on treatment with single-agent daratumumab or lenalidomide in case the other agent has to be permanently discontinued in absence of disease progression. If a patient on maintenance treatment must discontinue both, lenalidomide and daratumumab, they should be removed from the protocol therapy and proceed to event monitoring.

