## 8.2 Lenalidomide Dose Modifications

Lenalidomide (Days 1-21)	
Starting dose	10mg
-1	5 mg
-2	Discontinue

→ → Use the NCI Common Terminology Criteria for Adverse Events (CTCAE) version 4.0\*  
unless otherwise specified ← ←

CTCAE System/Organ/Class (SOC)	ADVERSE EVENT	AGENT	ACTION**

CTCAE System/Organ/Class (SOC)	ADVERSE EVENT	AGENT	ACTION**
Investigations	Platelet count decreased Grade 4	Lenalidomide	
*Omit dose until AE has resolved to Grade 1 or better
 
 
• Follow CBC weekly
 
• If thrombocytopenia <math><30,000/\text{mm}^3</math> recurs, reduce dose by one dose level (by 5 mg) and continue therapy when platelet count <math>\geq 30,000/\text{mm}^3</math>
 
 
If, after lenalidomide has been omitted, and the AE does not return to <math>\leq</math>Grade 1 within 4 weeks, then the patient may continue on single-agent daratumumab till the completion of maintenance and then proceed to Event Monitoring

	Neutrophil count decreased Grade 4		
*Omit dose until AE has resolved to Grade 2 or better
 
 
• Follow CBC weekly
 
* If neutropenia has resolved to <math>\leq</math>Grade 2, resume dose at one level lower
 
* If, after lenalidomide has been omitted, and the AE does not return to <math>\leq</math>Grade 1 within 4 weeks, then the patient may continue on single-agent daratumumab till the completion of maintenance and then proceed to Event Monitoring
 

Blood and lymphatic system disorders	Anemia Grade 4		
*Omit dose until AE has resolved to Grade 2 or better
 
 
• Follow CBC weekly
 
* If anemia has resolved to <math>\leq</math>Grade 2, resume dose at one level lower
 
* If, after lenalidomide has been omitted, and the AE does not return to <math>\leq</math>Grade 1 within 4 weeks, then the patient may continue on single-agent daratumumab till the completion of maintenance and then proceed to Event Monitoring
 

	Febrile neutropenia $\geq$ Grade 3		
 
• Omit dose and follow CBC weekly
 
• If neutropenia has resolved to <math>\leq</math>Grade 2, resume dose at same level with GCSF support (See Section 9.6)
 

CTCAE System/Organ/Class (SOC)	ADVERSE EVENT	AGENT	ACTION**

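### Criterion 3.28 ties the no-breast-feeding agreement to lenalidomide alone, so it misses pre-transplant daratumumab, the transplant period and later single-agent daratumumab (minor safety wording)

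*Combined protocol and SAP*

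**What the plan says.** Section 3.28 sits in the exclusion list. Its stated reason is that the study uses an investigational agent whose "genotoxic, mutagenic and teratogenic effects on the developing fetus and newborn are unknown". Of its three bullets, the second is "Nursing women (lactating females are eligible provided that they agree not to breast feed while taking lenalidomide". The other two, on pregnancy and on refusal of contraception, are not limited to one drug.

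The treatment schedule has four parts:

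- **Section 7.11, Consolidation 1:** daratumumab is the only agent listed, in cycles 1-2 or 1-4.
- **Section 7.12, Consolidation 2:** transplant, up to the Day 100 visit. No lenalidomide is listed.
- **Section 7.13, maintenance:** "All patients will be initiated on maintenance therapy as below within 14 days of completing Day 100 visit post-SCT". The table gives daratumumab with lenalidomide in cycles 4-15 (or 6-17).
- **Section 7.13, note:** from cycle 16 (or 18), patients still in response move to daratumumab alone every 3 months until progression or unwanted adverse events.

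For pregnancy, footnote i of the test schedule (Section 4.1) says a negative test "must be documented within 14 days of starting treatment on the study and for patients starting Cycle 4 (daratumumab+lenalidomide").

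**The concern.** The criterion exists to protect a fetus or newborn from the agent under study. Daratumumab is that agent: the primary objective (Section 2.1) concerns pre-transplant daratumumab consolidation, and dosing starts on Cycle 1 Day 1. Yet the only breast-feeding condition in the protocol text is tied to the other drug, which starts months later and stops while daratumumab continues. What is at stake is whether a safety condition matches its own purpose. No error rate or estimate is involved.

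**Working it through.** The plan states no figure to reproduce. The check compares the period that the agreement covers with the treatment schedule.

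**Inputs.** Cycle 1 (to 3) lasts 28 days (Section 7.11). "Cycle 2 (or 4, as the case may be for that patient) length = up to 84 days", made up of 28 days of treatment and a window of up to 56 days before transplant. Cycle 3 (or 5) lasts up to 124 days, because "Day 100 visit of ASCT occurs 90-110 days after ASCT + window period up to 14 days" before maintenance (110 + 14 = 124). Daratumumab is given on days 1, 8, 15 and 22 of cycles 1-2, and on days 1 and 15 of cycles 3-4.

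**Doses before transplant.**
- Two cycles: 4 + 4 = 8. The last dose is Cycle 2 Day 22, which is study day 28 + 22 = 50.
- Four cycles: 4 + 4 + 2 + 2 = 12. The last dose is Cycle 4 Day 15, which is study day 3 × 28 + 15 = 99.

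None of these doses falls in a lenalidomide cycle.

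**Elapsed time from Cycle 1 Day 1 to first lenalidomide** (nominal schedule, no dose holds). The minimum assumes no gap before transplant, the Day 100 visit on day 90, and maintenance starting at that visit.

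| | Minimum | Maximum |
|---|---|---|
| Two cycles | 28 + 28 + 90 = 146 days | 28 + 84 + 124 = 236 days |
| Four cycles | 3 × 28 + 28 + 90 = 202 days | 3 × 28 + 84 + 124 = 292 days |

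This is not time on drug. At the minimum, 90 of the days are the transplant cycle. At the maximum, 56 + 124 = 180 days are the pre-transplant window plus the transplant cycle. No study drug is scheduled in either.

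**Coverage by phase.**

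| Phase | Treatment | Within the agreement? |
|---|---|---|
| Cycles 1-2 (or 1-4) | Daratumumab | No |
| Cycle 3 (or 5) | Transplant | No |
| Cycles 4-15 (or 6-17) | Daratumumab + lenalidomide | Yes |
| Cycle 16 (or 18) onward | Daratumumab every 3 months | No |

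**Other sections.** The remaining reproductive safeguards (Sections 3.15, 4.1, 10.55 and 15.29) deal with pregnancy testing, pregnancy reporting and contraception. None restricts breast feeding. A line closing Section 8.2 speaks of lenalidomide being omitted during Consolidation 1, but the table in 7.11 lists daratumumab only, so that line does not bring the earlier period under the agreement.

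**Reach.** Section 16.73 expects about 40% women: 0.40 × 50 = 20. That says nothing about lactation.

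**The case against.** The strongest objection is that the bullet opens with nursing women as an exclusion. The natural reading bars a woman who is nursing at registration and admits one who still produces milk but has stopped. This stands. A reader might infer that the protocol lets women breast feed through consolidation from the start, and the text does not support that. What remains is narrower: a woman admitted as not nursing could resume outside the lenalidomide cycles and still keep her stated agreement.

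Reach is close to nil. Patients are transplant eligible after induction, and Section 1.2 gives a median age at diagnosis of 70. This also stands, and it limits the importance of the point without removing the mismatch.

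Consent and labelling may already cover the period. Sections 7.11 and 7.13 send daratumumab administration to the prescribing information and institutional guidelines, and Section 7.12 leaves transplant to institutional standards. A reader might infer that these women have no protection at all. The documents cannot show that, because those sources are not among them.

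Naming lenalidomide has a visible basis, since Section 15.27 carries its boxed warning on birth defects. That explains the wording, but the reason given in 3.28 is not confined to that drug.

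A reader might also count single-agent daratumumab after an early stop of lenalidomide. Section 8.1 says maintenance patients "may be continued on treatment with single-agent daratumumab or lenalidomide in case the other agent has to be permanently discontinued", but Section 13.3 sends patients to event monitoring after an omission of more than 28 days of either drug. The rules conflict, so the point does not rest on that route. The planned phase from cycle 16 (or 18) needs no such argument.

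The pregnancy-test footnote is only a modest comparison. It shows that the protocol recognises two treatment starts, but a test at a start is not continuous protection.

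Finally, eligibility acts at registration. The study was activated in April 2018 with about 2 years of planned accrual (Section 16.13), and Amendment 9 was pending after February 2021. Actual accrual status is not given, so an amended criterion may reach few or no new patients.

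**Conclusion.** The point holds as a minor safety-wording error. The agreement in 3.28 covers cycles 4-15 (or 6-17) only. It leaves out all 8 (or 12) pre-transplant daratumumab doses, the transplant period, and the open-ended single-agent daratumumab phase, although the criterion's reason is the unknown effect of the investigational agent on the newborn.

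A reader might take the 146-292 days as a duration of infant exposure. It is elapsed calendar time, much of it without scheduled study drug, and the documents contain no infant-exposure data.

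The conclusion assumes the nominal schedule and the reading that women nursing at registration are excluded. The figure of 0-1 affected patient in 50 is an assumption. Nothing here bears on sample size, endpoints or analysis.

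**What to change.** In 3.28, replace the words limiting the agreement to lenalidomide with: *from the first dose of daratumumab until the end of all protocol treatment (daratumumab, transplant and lenalidomide), and for any period after the last dose given in the prescribing information*. The documents do not state that later period, so it has to be taken from the labelling. The consent form should be checked for matching wording.

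The cost is one line in the next amendment. If accrual has closed, the same sentence would need to go in Section 7.0 to reach women still on treatment.
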